#### 4.1.8 Organ Function Requirements

##### 4.1.8.1 Adequate Bone Marrow Function Defined as:

- a. For patients with solid tumors without known bone marrow involvement:
  - Peripheral absolute neutrophil count (ANC)  $\geq 1000/\text{mm}^3$
  - Platelet count  $\geq 100,000/\text{mm}^3$  (transfusion independent, defined as not receiving platelet transfusions for at least 7 days prior to enrollment)
  - Hemoglobin  $\geq 8.0$  g/dL at baseline (may receive RBC transfusions)
- b. Patients with known bone marrow metastatic disease will be eligible for study if they meet the blood counts in 4.1.8.1.a (may receive transfusions provided they are not known to be refractory)

THIS PROTOCOL IS FOR RESEARCH PURPOSES ONLY, SEE PAGE 1 FOR USAGE POLICY

to red cell or platelet transfusions). These patients will not be evaluable for hematologic toxicity. At least 5 of every cohort of 6 patients must be evaluable for hematologic toxicity for the dose-escalation part of the study. If dose-limiting hematologic toxicity is observed, all subsequent patients enrolled on Part A must be evaluable for hematologic toxicity.

4.1.8.2 Adequate Renal Function Defined as:

- Creatinine clearance or radioisotope GFR  $\geq 70$  ml/min/1.73 m^2 or
- A serum creatinine based on age/gender as follows:

Age	Maximum Serum Creatinine (mg/dL)	
	Male	Female
1 to < 2 years	0.6	0.6
2 to < 6 years	0.8	0.8
6 to < 10 years	1	1
10 to < 13 years	1.2	1.2
13 to < 16 years	1.5	1.4
$\geq 16$ years	1.7	1.4

The threshold creatinine values in this Table were derived from the Schwartz formula for estimating GFR (Schwartz et al. J. Peds, 106:522, 1985) utilizing child length and stature data published by the CDC.

4.1.8.3 Adequate Liver Function Defined as:

- Total Bilirubin  $\leq 1.5 \times$  upper limit of normal (ULN) for age
- SGPT (ALT)  $\leq 3 \times$  ULN = 135 U/L. For the purpose of this study, the ULN for SGPT is 45 U/L.
- Serum albumin  $\geq 2$  g/dL.

4.1.8.4 Adequate Pancreatic Function Defined as:

- Serum amylase  $\leq 1.5 \times$  ULN
- Serum lipase  $\leq 1.5 \times$  ULN

4.1.9 Patients with seizure disorder may be enrolled if on anticonvulsants and well controlled.

4.1.10 Patients must be able to swallow tablets whole.

4.1.11 Part C: Archived paraffin-embedded tissue (20 unstained slides or a tumor block) from a prior resection must be available as a control for correlative studies. If tissue blocks or slides are unavailable, the study chair must be notified prior to enrollment.

4.1.12 Informed Consent: All patients and/or their parents or legally authorized representatives must sign a written informed consent. Assent, when appropriate, will be obtained according to institutional guidelines.

4.2 **Exclusion Criteria**

4.2.1 Pregnancy or Breast-Feeding

THIS PROTOCOL IS FOR RESEARCH PURPOSES ONLY, SEE PAGE 1 FOR USAGE POLICY

Pregnant or breast-feeding women will not be entered on this study, since there is yet no available information regarding human fetal or teratogenic toxicities. Based on its mechanism of action and findings in animals, selinexor may cause fetal harm when administered to a pregnant woman. Pregnancy tests must be obtained in girls who are post-menarchal. Males with female partners of reproductive potential or females of reproductive potential may not participate unless they have agreed to use two effective methods of birth control- including a medically accepted barrier method of contraceptive method (e.g., male or female condom) for the entire period in which they are receiving protocol therapy and for at least 1 week following their last dose of study drug. Abstinence is an acceptable method of birth control.

#### 4.2.2 Concomitant Medications

4.2.2.1 Corticosteroids: Patients receiving corticosteroids who have not been on a stable or decreasing dose of corticosteroid for at least 7 days prior to enrollment are not eligible. If used to modify **immune adverse events** related to prior therapy,  $\geq 14$  days must have elapsed since last dose of corticosteroid (See [Section 4.1.7.1.f](#)).

4.2.2.2 Investigational Drugs: Patients who are currently receiving another investigational drug are not eligible.

4.2.2.3 Anti-cancer Agents: Patients who are currently receiving other anti-cancer agents are not eligible.

4.2.3 Infection: Patients who have an uncontrolled infection are not eligible.

4.2.4 Patients who have received a prior solid organ transplantation are not eligible.

4.2.5 Patients who, in the opinion of the investigator, may not be able to comply with the safety monitoring requirements of the study are not eligible.

4.2.6 Patients with BMI < 3rd percentile for age, as defined by WHO criteria for patients 1-2 years of age and CDC criteria for patients > 2 years of age, are not eligible. (See [Appendix IX](#))

4.2.7 Patients with grade 3 ataxia or grade >1 extrapyramidal movement disorder are not eligible.

4.2.8 Patients with known macular degeneration, uncontrolled glaucoma, or cataracts are not eligible.

## 5.0 TREATMENT PROGRAM

### 5.1 Treatment Overview (Pre-Amendment #1):

Week	Day	Agent: Selinexor
1	1, 3 (Doses 1,2)	X
2	8, 10 (Doses 3,4)	X
3	15, 17 (Doses 5,6)	X
4	22, 24 (Doses 7,8)	X

Patients will receive selinexor twice weekly on a days 1,3 schedule (Mon/Wed, Tues/Thurs, or Wed/Fri). A cycle of therapy will be 28 days or 8 doses. The drug will be administered in tablet form with food. Patients may continue for a maximum of 24 cycles. Refer to [section 7.3](#) for recommended supportive care guidelines.

(Amendment #1):

Week	Day	Agent: Selinexor
1	1, 3 (Doses 1,2)	X
2	8, 10 (Doses 3,4)	X
3	15, 17 (Doses 5,6)	X
4	Rest	

With Amendment #1, patients will receive selinexor twice weekly on a days 1,3 schedule (Mon/Wed, Tues/Thurs, or Wed/Fri) on Weeks 1-3, followed by a one-week rest period. A cycle of therapy will be 28 days or 6 doses. The drug will be administered in tablet form with food. Patients may continue for a maximum of 24 cycles. Refer to [section 7.3](#) for recommended supportive care guidelines.

**Amendment #4:**

Week	Day	Agent: Selinexor
1	1	X
2	8	X
3	15	X
4	22	X

With Amendment #4, patients will receive selinexor once weekly, on Days 1, 8, 15, and 22 of a 28-day cycle. The drug will be administered in tablet form with food. Patients may continue for a maximum of 24 cycles. Refer to [Section 7.3](#) for recommended supportive care guidelines.

Drug doses should be adjusted based on the BSA calculated from height and weight measured within 7 days prior to the beginning of each cycle (See [Appendix VI](#)). If a dose is vomited within 30 minutes of administration and there is visible evidence of the tablet, the dose should be repeated. If the tablet is not visible, or the dose is vomited later than 30 minutes after administration, the dose should not be repeated. The patient/caregiver should make a note of the vomited dose and whether there is visible evidence of the tablet on the pill diary and proceed with the next dose at the next scheduled time of administration.

Selinexor is supplied by Karyopharm Therapeutics. **Do not use commercial supply.**

## 5.2 Criteria for Starting Subsequent Cycles

A cycle may be repeated every 28 days if the patient has at least stable disease and has again met laboratory parameters as defined in the eligibility section, [Section 4.0](#).

## 5.3 Dose Escalation Schema

### 5.3.1 Inter-Patient Escalation: Part A

The starting dose will be 35 mg/m^2 (dose level 1), with dose levels for subsequent groups of patients as follows.

(Pre-Amendment #4): Twice weekly dosing

THIS PROTOCOL IS FOR RESEARCH PURPOSES ONLY, SEE PAGE 1 FOR USAGE POLICY

Table for Dose Levels 1-3.

Dose Level**	Selinexor Dose (mg/m  )
-1	20
1*	35
2	45
3	60 ^

\* Starting Dose Level

^ Further dose escalation will be considered after evaluation of the pharmacokinetics and toxicity profile**Amendment #4:** Once weekly dosing

Table for Dose Levels 1 & 2:

Dose Level**	Selinexor Dose (mg/m  )
-1	35
1*	45
2	55

\* Starting Dose Level

**Amendment #4:** With amendment #4, the starting dose will be 45 mg/m^2. Prophylactic treatment of nausea and emesis (such as 5-HT3 antagonists +/- another agent [e.g., dexamethasone, NK1 receptor antagonist, etc]) is strongly recommended during Cycles 1 and 2 (see [Section 7.3](#)). In adult patients, double antiemetic coverage (5HT3 antagonist + another agent) is preferred. If DLT of vomiting or dehydration is experienced in  $\geq 2/6$  evaluable patients at a dose level outlined in the dose level tables above, the dose level will be repeated with required maximal antiemetic therapy (5-HT3 antagonist PLUS antiemetic agent(s)) prior to each dose during Cycles 1 and 2. Once the requirement for prophylaxis during Cycles 1 and 2 has been made, this will be carried forward for all subsequent patients entered at the same or higher dose level. Dose levels which require antiemetic prophylaxis will be denoted with the suffix letter "A" (e.g. Dose Levels -1A, 1A, or 2A).

Selinexor is supplied by Karyopharm Therapeutics. **Do not use commercial supply.**

5.3.2 Part B: Non-Surgical HGG Expansion Cohort

Patients with HGG not requiring resection will be treated at the recommended phase 2 dose (RP2D) determined from the phase 1 component (Part A) of this trial.

5.3.3 Part C: Surgical HGG Expansion Cohort

Patients with HGG requiring resection (Part C) will be treated at the recommended phase 2 dose (RP2D) determined from the phase 1 component (Part A) of this trial for 2 doses prior to undergoing scheduled resection of their tumors (*i.e.* Surgical resection should occur after dose on Day 8 but before dose on Day 15 of Cycle 1). After recovery from surgery with wound healed (minimum 3 weeks) and meeting criteria in [Section 5.2](#), patients can resume selinexor at the same dose and schedule and continue therapy to complete Cycle 1 and continue with Cycle 2. Patients who fail to recover from surgery within 6 weeks will be removed from protocol therapy.

5.3.4 Intra-Patient Escalation

Intra-patient dose escalation is not allowed.

#### 5.4 Grading of Adverse Events

Adverse events (toxicities) will be graded according to the NCI Common Terminology Criteria for Adverse Events (CTCAE) version 5.0. All appropriate treatment areas should have access to a copy of the CTCAE version 5.0. A copy of the CTCAE version 5.0 can be downloaded from the CTEP website ([http://ctep.cancer.gov/protocolDevelopment/electronic\\_applications/ctc.htm](http://ctep.cancer.gov/protocolDevelopment/electronic_applications/ctc.htm)). Any suspected or confirmed dose-limiting toxicity should be reported immediately (within 24 hours) to the Study Chair.

#### 5.5 Definition of Dose-Limiting Toxicity (DLT)

DLT will be defined as any of the following events that are possibly, probably or definitely attributable to selinexor. The DLT observation period for the purposes of dose-escalation will be the first cycle of therapy.

Dose limiting hematological and non-hematological toxicities are defined differently.

##### 5.5.1 Non-hematological dose-limiting toxicity

- Any Grade 4 non-hematological toxicity
- Any Grade 3 non-hematological toxicity with the specific exception of:
  - Grade 3 nausea, vomiting, or dehydration that resolves to Grade  $\leq 2$  within 3 days. For the purposes of this pediatric study, tube feeding should not be considered a Grade 3 DLT. See [Section 7.3](#) for supportive care guidelines.
  - Grade 3 anorexia. See [Section 7.3](#) for supportive care guidelines
  - Grade 3 weight changes. See [Section 7.3](#) for supportive care guidelines.
  - Grade 3 diarrhea that resolves to Grade  $\leq 2$  within 7 days
  - Grade 3 liver enzyme elevation, including ALT/AST/GGT that returns to levels that meet initial eligibility criteria or baseline within 7 days. See [Appendix VIII](#) for values that represent thresholds between CTCAE grades.
  - Grade 3 bilirubin that returns to meet eligibility criteria within 7 days. See [Appendix VIII](#) for values that represent thresholds between CTCAE grades.
  - Grade 3 infection of  $< 5$  days duration
  - Grade 3 hypophosphatemia, hypokalemia, hypocalcemia, hypomagnesemia, or asymptomatic hyponatremia responsive to oral supplementation
- Fever greater than  $40^{\circ}\text{C}$  of  $\geq 5$  days duration will be considered dose-limiting
- Any  $\geq$  grade 2 non-hematological toxicity that persists for  $\geq 7$  days and is considered sufficiently medically significant or sufficiently intolerable by patients that it requires two doses omitted in a cycle.
- Any toxicity that requires treatment interruption as outlined in [Sections 6.3-6.7](#) and does not resolve within the specified time frame will be considered dose-limiting.

##### 5.5.2 Hematological dose limiting toxicity

In patients evaluable for hematological toxicity (See [Section 4.1.8.1](#)),

THIS PROTOCOL IS FOR RESEARCH PURPOSES ONLY, SEE PAGE 1 FOR USAGE POLICY

- Grade 4 thrombocytopenia (platelet count  $< 25,000/\text{mm}^3$ ), Grade 4 anemia, or Grade 4 neutropenia, not due to malignant infiltration
- Grade 3 thrombocytopenia that persists for  $\geq 7$  days
- Grade 3 thrombocytopenia requiring a platelet transfusion on 2 separate days, within a 7 day period
- Grade 3 thrombocytopenia with clinically significant bleeding, petechiae or purpura
- Myelosuppression that causes a delay of  $>14$  days between treatment cycles.

## 6.0 DOSE MODIFICATIONS FOR ADVERSE EVENTS

**The Study Chair and Vice Chair must be notified of any dosage modification or use of myeloid growth factor.**

### 6.1 Dose Modifications for Hematological Toxicity

- 6.1.1 If a patient experiences Grade 4 neutropenia, selinexor should be held. Institute short acting granulocyte colony stimulating factor (filgrastim or biosimilar) as per institutional guidelines. Counts should be checked every 2 – 3 days until recovery to Grade  $\leq 2$  or baseline and without fever (if febrile) and the patient is clinically stable. If this is a first occurrence, and myelosuppression has lasted  $\leq 7$  days, the patient may continue at the same dose. If lasting for  $> 7$  days or this is a second occurrence resulting in a missed dose, reduce selinexor by 1 dose level. If the occurrence falls on Day 1 of a cycle, delay start of the cycle, institute short acting granulocyte colony stimulating factor as per institutional guidelines, and check neutrophils every 2 – 3 days until recovery to Grade  $< 2$  and eligibility is met to begin the next cycle. If the toxicity recurs, the patient may resume treatment at the currently assigned dose with a change in the schedule to weekly dosing for 3 weeks followed by a 1 week rest.
- 6.1.2 If a patient experiences either Grade 4 or dose-limiting Grade 3 thrombocytopenia as defined in [Section 5.5.2](#), selinexor should be held. Counts should be checked every 2 – 3 days until any bleeding has stopped, patient is clinically stable, and the platelets have recovered to meet eligibility to begin the next cycle. When resuming selinexor, reduce by 1 dose level. If the occurrence falls on Day 1 of a cycle, delay start of the cycle and check platelet counts every 2 – 3 days until the platelets have recovered to meet eligibility to begin the next cycle. When resuming selinexor, reduce by 1 dose level. If the toxicity recurs, the patient may resume treatment at the currently assigned dose with a change in the schedule to weekly dosing for 3 weeks followed by a 1-week rest.
- 6.1.3 If a patient experiences myelosuppression not otherwise specified above that causes a delay of  $>14$  days between treatment cycles, counts should be checked every 3 – 4 days for thrombocytopenia and for neutropenia during this time. Upon resolution to eligibility criteria, the patient may resume the subsequent cycle reduced by one dose level. If the toxicity recurs, the patient may resume treatment at the currently assigned dose with a change in the schedule to weekly dosing for 3 weeks followed by a 1 week rest.

THIS PROTOCOL IS FOR RESEARCH PURPOSES ONLY, SEE PAGE 1 FOR USAGE POLICY

- 6.1.4 Patients who experience Grade 4 anemia that is at least possibly attributable to selinexor must be removed from protocol therapy.
- 6.1.5 If toxicity does not resolve to meet starting parameters ([section 5.2](#)) within 21 days after the planned start of the next treatment cycle, the patient must be removed from protocol therapy.
- 6.1.6 If dose-limiting hematological toxicity recurs in a patient who has resumed treatment at Dose Level -1 and is already on the modified selinexor dosing schedule (3 weeks on/1 week off), the patient must be taken off protocol therapy.

## 6.2 Dose Modifications for Non-Hematological Dose-Limiting Toxicity

- 6.2.1 If a patient experiences non-hematological dose-limiting toxicity as defined in [Section 5.5.1](#), the treatment will be held. If the toxicity resolves to meet eligibility parameters or baseline within 14 days after the planned start of the next treatment cycle, the patient may resume treatment reduced by one dose level. If the toxicity recurs, the patient may resume treatment at the currently assigned dose with a change in the schedule to weekly dosing for 3 weeks followed by a 1 week rest. Dosing schedules modified for toxicity will not be re-escalated, even if there is minimal or no toxicity with the modified dose.
  - 6.2.1.1 Note that patients who experience Grade  $\geq 3$  anaphylaxis should be permanently removed from protocol therapy and should not resume treatment.
- 6.2.2 If toxicity does not resolve to meet eligibility or baseline parameters within 21 days after the planned start of the next treatment cycle, the patient must be removed from protocol therapy.
- 6.2.3 If the same dose-limiting toxicity recurs in a patient who has resumed treatment at Dose Level -1 and is already on the modified selinexor dosing schedule (3 weeks on/1 week off), the patient must be taken off protocol therapy.

## 6.3 Dose Modifications for Anorexia/Weight Loss

- 6.3.1 Anorexia and weight loss are anticipated toxicities and should be proactively managed. If a patient experiences Grade 3 anorexia or weight loss, dosing should continue as planned and maximal supportive care (e.g. appetite stimulants, nutritional supplements, tube feeding) should be implemented as outlined in [Section 7.3.1](#).

## 6.4 Dose Modifications for Nausea/Vomiting/Dehydration

If a patient experiences Grade 3 nausea, vomiting, or dehydration, the treatment will be held. Patients should be treated with anti-emetic therapy as outlined in [Section 7.3.2](#). If toxicity resolves to Grade  $\leq 2$  nausea/vomiting/dehydration within 3 days, drug may resume at same dose. Grade 3 nausea, vomiting, or dehydration that persists  $\geq 3$  days will be considered dose-limiting and require dose modification per [Section 6.2](#).

## 6.5 Dose Modifications for Diarrhea

THIS PROTOCOL IS FOR RESEARCH PURPOSES ONLY, SEE PAGE 1 FOR USAGE POLICY

Grade	Action	Dose Modification
Grade 1	
 
Dietary recommendations: avoid lactose containing foods, apple juice
 
	Maintain dose.
Grade 2	
 
Dietary recommendations: avoid lactose containing foods, apple juice, “BRAT” diet
 
Rule out other causes of diarrhea, including infectious agents. In case of opportunistic infection, withdraw all steroids (with tapering if medically appropriate) until culture is negative.
 
Institute standard anti-diarrheal therapy with loperamide (see Appendix X)
 
After the first occurrence of diarrhea, loperamide can be considered prophylactically approximately 1 – 2 hours before the administration of selinexor and repeated every 4 hours for the first 12 hours
 
	Maintain dose.
Grade 3/4	
 
Dietary recommendations: avoid lactose containing foods, apple juice, “BRAT” diet
 
Rule out other causes of diarrhea, including infectious agents. In case of opportunistic infection, withdraw all steroids (with tapering if medically appropriate) until culture is negative
 
Institute standard anti-diarrheal therapy with loperamide (see Appendix X)
 
After the first occurrence of diarrhea, loperamide should be considered prophylactically approximately 1 – 2 hours before the administration of selinexor and repeat every 4 hours for the first 12 hours
 
	Hold selinexor until Grade $\leq 2$ . If $> 7$ days, resume at lower dose level.

If a patient experiences Grade  $\geq 3$  diarrhea, treatment will be held. If diarrhea resolves to Grade  $\leq 2$  within 7 days, the drug may be resumed at the same dose. Grade  $\geq 3$  diarrhea that persists  $\geq 7$  days will be considered dose-limiting and require dose modification per [Section 6.2](#). If Grade  $\geq 3$  diarrhea recurs at the lower dose and persists  $\geq 7$  days despite maximal use of antidiarrheal therapy, the patient will be removed from protocol therapy.

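### After a first attributable Grade 4 diarrhea event that improves quickly, Sections 6.2.1 and 6.5 give different re-dosing rules, in dose and in recovery threshold, and nothing says which governs

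*Combined protocol and SAP*

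**What the plan says.** Section 5.5 limits DLTs to events "possibly, probably or definitely attributable to selinexor". Within that, Section 5.5.1 lists "Any Grade 4 non-hematological toxicity" with no condition on duration. Its exceptions attach to Grade 3 only; the diarrhea one begins "Grade 3 diarrhea that resolves to Grade" and requires improvement to Grade 2 or less within 7 days. The last bullet of 5.5.1 refers to Sections 6.3–6.7: a toxicity that requires interruption there "and does not resolve within the specified time frame will be considered dose-limiting".

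Section 6.2.1 applies to any non-hematological DLT defined in 5.5.1. Treatment is held. If the toxicity recovers to eligibility parameters or baseline within the stated window, "the patient may resume treatment reduced by one dose level". Recurrence is handled differently: "If the toxicity recurs, the patient may resume treatment at the currently assigned dose with a change in the schedule".

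Section 6.5 has a single table row for Grade 3/4 diarrhea: hold until Grade 2 or less, and only if this takes more than 7 "days, resume at lower dose level". The text below the table, for Grade 3 or higher, says that if diarrhea improves to Grade 2 or less "within 7 days, the drug may be resumed at the same dose". Only diarrhea persisting 7 days or longer is sent to Section 6.2. Sections 6.7.1 (bilirubin, Grade 2 or higher) and 6.7.2 (ALT/AST, Grade 3 or higher) follow the same pattern but require recovery to Grade 1 or less.

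**The concern.** A brief Grade 4 diarrhea event is a DLT under 5.5.1, so it falls under 6.2.1. It also lies squarely within the wording of 6.5, which permits what 6.2.1 does not offer: the full dose, and at Grade 2 rather than at baseline.

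Dosing is weekly (Section 5.1, Amendment #4). A child with Grade 4 diarrhea after the Day 1 dose who has reached Grade 2 by Day 8 could be given the full Day 8 dose under 6.5. Under 6.2.1 the child would wait for fuller recovery and restart one level lower. Two sites could treat the same child differently, each following the protocol. What is at stake is that child's safety after a severe attributable toxicity.

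**Working it through.** The plan states no figure to reproduce. The check follows one event through both routes: a first Grade 4 diarrhea event, at least possibly attributable, improving to Grade 2 or less within 7 days.

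| Step | 5.5.1 then 6.2.1 | 6.5 |
|---|---|---|
| Is Grade 4 covered? | Yes, any Grade 4; the diarrhea exception is Grade 3 only | Yes, row for Grade 3/4, text for Grade 3 or higher |
| Does short duration matter? | No | Yes, it keeps the event out of 6.2 |
| Recovery needed to resume | Eligibility parameters or baseline | Grade 2 or less |
| Dose on resumption | One level lower | Same dose allowed |

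For Grade 3 diarrhea with the same course the routes agree, because 5.5.1 exempts it. The conflict is confined to Grade 4.

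**Does any text resolve it?** The last bullet of 5.5.1 only adds DLTs (interruptions that do not resolve in time); it does not exempt a Grade 4 event that does. Section 6.4 avoids the problem because its same-dose rule names Grade 3 only. No section states that 6.5 overrides 6.2, or the reverse.

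**Size of the dose difference** (levels from Section 5.3.1, Amendment #4; tablet doses from Appendix VI):
- 55/45 = 1.222, so the same dose is 22% above the reduced dose.
- 45/35 = 1.286, so 29% above.
- At BSA 1.50 m²: 80 − 65 = 15 mg, or 65 − 50 = 15 mg, per weekly dose.
- No level is listed below 35 mg/m², so at that level 6.2.1 has no reduced dose to offer.

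**Frequency.** Sections 2.4 and 2.8 report no Grade 3 or 4 non-hematologic events among 30 adults on 80 mg weekly (about 45 mg/m²). Exact 95% upper bounds for 0/30:
- one-sided: 1 − 0.05^(1/30) = 9.5%
- two-sided: 1 − 0.025^(1/30) = 11.6%

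These bounds cover all such events together; Grade 4 diarrhea is only a part. The data are not pediatric and do not cover 55 mg/m². The documents give no pediatric figure for weekly dosing.

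**Hepatic events** (Appendix VIII). To go from Grade 4 to Grade 1 or less within 7 days:
- ALT must fall from above 900 to at most 135 U/L: 1 − 135/900 = 85%
- AST from above 1000 to at most 150 U/L: 1 − 150/1000 = 85%
- bilirubin from above 10× to at most 1.5×: 1 − 1.5/10 = 85%

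Each is a fall of more than 85% in a week, so the conflict on dose exists there but will seldom arise.

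**The case against.** The best defence is that 6.2 is the general rule and 6.5 the specific one, so 6.5 governs. Section 6.5 says twice, in the table and in the text, that duration triggers the reduction, and it states when a patient passes to 6.2. Section 6 also does not tie DLT status to one dosing action: Grade 4 neutropenia is a DLT, yet 6.1.1 allows the same dose after a first occurrence lasting 7 days or less, while Grade 4 anemia means removal (6.1.4). Where severity was meant to force a reduction, the plan says so, as for sodium at or below 125 mmol/L in 6.6.

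This is a workable reading, and the sponsor may have meant it. But the plan nowhere states that the specific section prevails. Section 6.1.1 is a hematological rule outside 6.2 and does not say how 6.2.1 and 6.5 fit together. The Grade 3 limit in both 6.4 and the 5.5.1 diarrhea exception points the other way.

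The objection is right that the effect is small. Both rules are permissive. Suspected DLTs go to the Study Chair within 24 hours (5.4), and DLT evaluations are reviewed weekly (14.4.2). Central input before the next dose is therefore likely, although neither section requires a reduction.

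A reader might also infer that sites can simply reduce the dose and satisfy every section. The documents do not support that: a reduced dose given at Grade 2 may still fall short of the recovery required by 6.2.1, and at 35 mg/m² there is no listed level to drop to.

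**Conclusion.** The contradiction stands. For a first attributable Grade 4 diarrhea event that improves to Grade 2 or less within 7 days, 6.2.1 and 6.5 differ in both dose and recovery threshold, and nothing sets precedence. The dose gap is 10 mg/m², or 22% to 29%. The hepatic conflict concerns dose only and adds little weight.

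A reader might infer that the escalation decision is compromised. It is not: DLT counting is set by 5.5 and the MTD by 11.2.2, and a Cycle 1 Grade 4 event counts as a DLT whatever dose follows. Nor does the conflict on dose extend to recurrence, where 6.2.1 itself keeps the assigned dose and changes the schedule. Events not attributable to selinexor are outside it.

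This is a low-priority patient-safety correction. The expectation that the event is uncommon rests on 30 adults at one weekly dose; the existence of the conflict does not depend on that figure.

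**What to change.** Keep the hold as written. Limit the same-dose provision to Grade 3 in 6.5 (table row and text) and in 6.7.2, and to Grade 2–3 in 6.7.1. Then add to 6.5 and 6.7:

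*Grade 4 events at least possibly attributable to selinexor are dose-limiting under Section 5.5.1 whatever their duration; recovery and resumption follow Section 6.2, except that the removal rule in Section 6.5 for Grade ≥3 diarrhea that recurs at the lower dose and persists ≥7 days still applies.*

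The exception is needed because 6.2.1 would otherwise allow such a patient to continue on a changed schedule. The sentence should not restate the one-level reduction, since 6.2.1 treats recurrence differently and no level is listed below 35 mg/m².

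If the sponsor intends the same dose after a brief Grade 4 event, that is a policy choice, and the exception should instead be written into 6.2.1. Either route costs a short wording amendment, with no change to sample size, visits or data collection.
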